 - b. Family history (coronary heart disease in a first degree relative, men <45 years; women <55 years);
 - c. Smoking (current smoker);
 - d. Hypertension (Systolic blood pressure ≥ 140 mmHg, diastolic blood pressure ≥ 90 mmHg and/or on antihypertensive medications) at Week -2 (Visit S1);
 - e. Low HDL-C (<40 mg/dL) at Week -2 (Visit S1);
 - f. Coronary calcium score $>95\%$ for age/sex (see [Appendix 6](#)).

Exclusion Criteria:

1. Total fasting (minimum of 10 hours) TG ≥ 500 mg/dL (5.6 mmol/L) at Week -2 (Visit S1).
Note: If a patient fails to meet TG criterion, an optional single repeat visit/measurement can, at the discretion of the investigator, be completed up to a maximum of 10 days later. For those patients who have a repeat TG measurement, the repeat value will be used to determine eligibility.
2. Renal dysfunction or nephritic syndrome or a history of nephritis, including estimated glomerular filtration rate (eGFR) (using central laboratory determined Modification of Diet in Renal Disease [MDRD] formula) <30 mL/min/1.73 m² at Week -2 (Visit S1) ([Levey 2006](#)).
Note: If a patient fails to meet eGFR criterion, an optional single repeat visit/measurement can, at the discretion of the investigator, be completed up to a maximum of 10 days later. For those patients who have a repeat eGFR measurement, the repeat value will be used to determine eligibility.
3. Body mass index (BMI) ≥ 40 kg/m²;
4. Recent (within 3 months prior to the screening visit [Week -2 (Visit S1)] or between screening and randomization visits) myocardial infarction (MI), unstable angina leading to hospitalization, uncontrolled, symptomatic cardiac arrhythmia (or medication for an arrhythmia that was started or

dose changed within 3 months of screening), CABG, PCI, carotid surgery or stenting, cerebrovascular accident, transient ischemic attack (TIA), endovascular procedure or surgical intervention for peripheral vascular disease, or plans to undergo a major surgical or interventional procedure (e.g., PCI, CABG, carotid or peripheral revascularization). Patients with implantable pacemakers or automatic implantable cardioverter defibrillators may be considered if deemed by the Investigator to be stable for the previous 3 months.

5. Uncontrolled hypertension, defined as sitting systolic blood pressure (SBP) ≥ 160 mmHg and diastolic blood pressure (DBP) ≥ 100 mmHg after sitting quietly for 5 minutes.

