Note: If a patient fails to meet SBP and/or DBP criteria, an optional single repeat visit/measurement can, at the discretion of the investigator, be completed up to a maximum of 10 days later. For those patients who have a repeat blood pressure measurement, the repeat value will be used to determine eligibility.

6. Uncontrolled diabetes including hemoglobin A_{1C} (HbA_{1C}) $\geq 10\%$ at Week -2 (Visit S1);
7. Uncontrolled hypothyroidism, including thyroid-stimulating hormone (TSH) $>1.5 \times$ the upper limit of normal (ULN) at Week -2 (Visit S1);
8. Liver disease or dysfunction, including:

- Positive serology for hepatitis B surface antigen (HBsAg) and/or hepatitis C antibodies (HCV-AB) at Week -2 (Visit S1), or
- Alanine aminotransferase (ALT), aspartate aminotransferase (AST) $\geq 2 \times$ ULN, and/or total bilirubin (TB) $\geq 2 \times$ ULN at Week -2 (Visit S1). If TB $\geq 1.2 \times$ ULN, a reflex indirect (unconjugated) bilirubin will be obtained and if consistent with Gilbert's disease or if the patient has a history of Gilbert's Disease, the patient may be enrolled in the study.

Note: If a patient fails to meet ALT and/or AST criteria, an optional single repeat visit/measurement can, at the discretion of the investigator, be completed up to a maximum of 10 days later. For those patients who have a repeat ALT and/or AST measurement, the repeat value will be used to determine eligibility. Also, if test for hepatitis C antibody is positive, but optional reflexive test for hepatitis C ribonucleic acid (RNA) is negative, patient can be enrolled.

9. Gastrointestinal conditions or procedures (including weight loss surgery; e.g., Lap-Band® or gastric bypass) that may affect drug absorption;
10. Hematologic or coagulation disorders or a hemoglobin (Hgb) level <10.0 g/dL (100 g/L) at Week -2 (Visit S1);
11. Active malignancy, including those requiring surgery, chemotherapy, and/or radiation in the past 5 years. Nonmetastatic basal or squamous cell carcinoma of the skin and cervical carcinoma in situ are allowed;
12. Unexplained creatine kinase (CK) $>3 \times$ ULN at screening up to randomization (ie, not associated with recent trauma or physically strenuous activity). Patients with an explained CK elevation must have single repeat CK $\leq 3 \times$ ULN prior to randomization;

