7.2. Patient Exclusion Criteria

1. Total fasting (minimum of 10 hours) TG \geq 500 mg/dL (5.6 mmol/L) at Week -2 (Visit S1).

Note: If a patient fails to meet TG criterion, an optional single repeat visit/measurement can, at the discretion of the investigator, be completed up to a maximum of 10 days later. For those patients who have a repeat TG measurement, the repeat value will be used to determine eligibility.

2. Renal dysfunction or nephritic syndrome or a history of nephritis, including estimated glomerular filtration rate (eGFR) (using central laboratory determined Modification of Diet in Renal Disease [MDRD] formula) $<$ 30 mL/min/1.73 m² at Week -2 (Visit S1) ([Levey 2006](#)).

Note: If a patient fails to meet eGFR criterion, an optional single repeat visit/measurement can, at the discretion of the investigator, be completed up to a maximum of 10 days later. For those patients who have a repeat eGFR measurement, the repeat value will be used to determine eligibility.

3. Body mass index (BMI) $\geq 40 \text{ kg/m}^2$;
4. Recent (within 3 months prior to the screening visit [Week -2 (Visit S1)] or between screening and randomization visits) myocardial infarction (MI), unstable angina leading to hospitalization, uncontrolled, symptomatic cardiac arrhythmia (or medication for an arrhythmia that was started or dose changed within 3 months of screening), CABG, PCI, carotid surgery or stenting, cerebrovascular accident, transient ischemic attack (TIA), endovascular procedure or surgical intervention for peripheral vascular disease, or plans to undergo a major surgical or interventional procedure (e.g., PCI, CABG, carotid or peripheral revascularization). Patients with implantable pacemakers or automatic implantable cardioverter defibrillators may be considered if deemed by the Investigator to be stable for the previous 3 months.
5. Uncontrolled hypertension, defined as sitting systolic blood pressure (SBP) $\geq 160 \text{ mmHg}$ and diastolic blood pressure (DBP) $\geq 100 \text{ mmHg}$ after sitting quietly for 5 minutes.

Note: If a patient fails to meet SBP and/or DBP criteria, an optional single repeat visit/measurement can, at the discretion of the investigator, be completed up to a maximum of 10 days later. For those patients who have a repeat blood pressure measurement, the repeat value will be used to determine eligibility.

6. Uncontrolled diabetes including hemoglobin A_{1C} (HbA_{1C}) $\geq 10\%$ at Week -2 (Visit S1);

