16. Previous enrollment in a BA clinical study;
17. Use of any of the following drugs within 5 weeks prior to screening (Visit S1) unless otherwise stated or a plan to use these drugs during the study is **prohibited**:
 - Systemic corticosteroids. Topical and inhaled corticosteroids are allowed.
 - Simvastatin ≥ 40 mg/day;
 - Non-statin LDL-C-modifying therapies:
 - Fibrates (including fenofibrate);
 - Niacin and derivatives;
 - Bile acid sequestrants;
 - Ezetimibe;
 - Mipomersen or lomitapide (6 months prior to screening);
 - Apheresis;
 - PCSK9 inhibitors (4 months prior to screening except PCSK9 small interfering RNA (siRNA), which are prohibited if used at any time in the past);
 - Cholesteryl ester transfer protein (CETP) inhibitors (12 months prior to screening);
 - Red yeast rice extract-containing products (2 weeks prior to screening);
18. Starting or adjusting the dose of the following permitted drugs within 5 weeks prior to screening. These drugs are **allowed as long as stable** at least 5 weeks prior to screening (Visit S1) unless otherwise noted:
 - Hormone replacement;
 - Thyroid replacement;

- Obesity medication (6 months prior to screening);
- Omega 3 fatty acids;
- Diabetes medications;

19. Previous intolerance to ezetimibe;

20. A medical or situational (ie, geographical) finding that in the investigator's opinion may compromise the patient's safety or ability to complete the study;

21. An employee or contractor of the facility conducting the study, or a family member of the Principal Investigator, Co-Investigator, or Sponsor.

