10.5.1. Screening Week -2 (Visit S1; Day -16 to Day -5)

The screening period will begin with a screening visit that will occur within approximately 2 weeks prior to randomization. Visit S1 will allow the investigator to assess the patient's preliminary eligibility. After the patient provides written informed consent (see Section 10.1), the patient will undergo the following assessments and procedures:

- Assess AEs and serious adverse events (SAEs) (starting from signing the informed consent document);
- Demographics;
- Clinically relevant medical history;

- Prior and concomitant medication review;
- Review of all inclusion/exclusion criteria that can be assessed at this time;
- Height (cm), and weight (kg);
- Vital signs;
- Central clinical laboratory evaluations:
 - TSH;
 - Hematology, blood chemistry, and urinalysis;
 - Serology (including HBsAg, hepatitis C virus [HCV] antibody);
 - Basic fasting lipids (TC, calculated LDL-C, HDL-C, non-HDL-C, and TG);
 - Serum pregnancy test (in female patients of childbearing potential) or FSH (only in postmenopausal women <55 years of age);
 - HbA_{1C};
- Contact IWRS to register the patient.

Patients who meet all enrollment criteria that can be assessed following review of the Visit S1 central clinical laboratory results (available several days after Visit S1) will be instructed to return for Visit T1 and to maintain consistent diet and exercise patterns throughout the study. Patients who fail to meet any entry criterion that can be assessed at Visit S1 are considered to be screen failures and are not required to return for additional visits (although a patient can be seen at any time for safety reasons).

Note: An unscheduled visit may be completed no more than 10 days after the screening visit if patient fails to meet entry criteria for LDL-C, TG, DBP, SBP, eGFR, ALT, AST, serology and/or CK entry criterion at the discretion of the investigator if warranted. For those patients who have a repeat measurement, the repeat value will be used to determine eligibility.

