10.6. Discontinuations

10.6.1. Patients Inadvertently Enrolled

The inclusion and exclusion criteria for enrollment must be followed exactly and completely. If a patient who does not meet enrollment criteria is inadvertently enrolled, the Medical Monitor should be contacted within 24 hours of identification. If it is determined after discussion with the Medical Monitor that, in considering patient safety, it is appropriate to continue IMP (documentation of this is necessary), the patient will continue on IMP and be monitored for all visits and testing (including laboratory measures) for the duration of the study. If after discussion with the Medical Monitor it is determined that the patient should not continue IMP, IMP will be discontinued, but the patient will remain in the study to be evaluated for concomitant medications, and efficacy and safety endpoints until the end of the study visit.

Patients inadvertently enrolled under the following criteria should be discontinued from IMP (but remain in the study):

- Female patients who are pregnant or are breastfeeding or who do not agree to use at least 1 reliable methods of birth control during the study (unless they have agreed to follow the definition of true abstinence);
- Any clinically significant medical condition that according to the investigator could interfere with participation in the study;
- Unable or unwilling to comply with protocol requirements, or deemed by the investigator to be unfit for the study;
- Have a history of drug, alcohol, or substance abuse within the past 6 months, as assessed by the investigator.

If a patient stops IMP for any of the above exclusion criteria following discussion with the Medical Monitor, then investigators should notify the Sponsor (or designee). The reason for the patient's inadvertent enrollment should be documented in the patient's record.

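### Exclusion 5 requires SBP ≥160 mmHg and DBP ≥100 mmHg together, but its own note treats each pressure as failable on its own; the two should be aligned, preferably with *and/or* in the definition

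*Protocol*

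**What the plan says.** The definition reads "Uncontrolled hypertension, defined as sitting systolic blood pressure (SBP) ≥ 160 mmHg and diastolic blood pressure (DBP) ≥ 100 mmHg", measured after five minutes of quiet sitting. It appears in the Synopsis and again in Section 7.2, with *and* as the connector both times.

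The note under the criterion, also in both places, begins "If a patient fails to meet SBP and/or DBP criteria" and allows one optional repeat within 10 days at the investigator's discretion. It ends: "For those patients who have a repeat blood pressure measurement, the repeat value will be used to determine eligibility".

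Section 10.5.1 allows an unscheduled visit "if patient fails to meet entry criteria for LDL-C, TG, DBP, SBP, eGFR, ALT, AST, serology and/or CK entry criterion", listing the two pressures as separate items. The same section states: "Patients who fail to meet any entry criterion that can be assessed at Visit S1 are considered to be screen failures". Section 10.6.1 adds: "The inclusion and exclusion criteria for enrollment must be followed exactly and completely".

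Amendment 1 does not touch exclusion 5. The SAP has no blood-pressure entry rule of its own; SAP 5.2.3 assesses entry violations against the protocol's criteria.

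**The concern.** If both limits must be reached, a patient with one raised pressure has failed nothing and needs no repeat, so the *or* in the note has almost no work to do. If one raised pressure counts as a failure, the definition carries the wrong connector. A site cannot follow the criterion exactly while it and its note point in different directions.

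Two things are at stake.

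- **Consistency.** About 125 sites are planned (Section 6.4). One could randomize a patient at 190/95 mmHg on the definition while another records a screen failure on the note. The ambiguity then carries into the entry-deviation tables under SAP 5.2.3.
- **Safety.** Exclusion 5 is the only blood-pressure safety limit at entry in either document, and the population has ASCVD, HeFH or multiple cardiovascular risk factors. Read literally, it puts no ceiling on SBP while DBP is below 100 mmHg, and none on DBP while SBP is below 160 mmHg.

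**Working it through.** **Logic check.** The plan gives no figure to reproduce. There are four possible blood-pressure patterns:

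| SBP (mmHg) | DBP (mmHg) | Definition (*and*) | Note (*and/or*) | Agree? |
|---|---|---|---|---|
| ≥160 | ≥100 | excluded | criterion failed | yes |
| ≥160 | <100 | not excluded | criterion failed, repeat allowed | no |
| <160 | ≥100 | not excluded | criterion failed, repeat allowed | no |
| <160 | <100 | not excluded | not failed | yes |

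The texts diverge in two of the four patterns, those with exactly one raised pressure. Take 190/95 mmHg. Under the definition the patient is eligible. Under the note the patient has failed the SBP criterion and, without a passing repeat, becomes a screen failure under Section 10.5.1.

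**Size of the disputed group (illustration only).** All inputs are assumptions. Screening SBP and DBP are taken as bivariate normal, with SBP mean 125 to 135 and SD 14 to 18, DBP mean 75 to 80 and SD 9 to 11, and correlation ρ 0.5 to 0.7.

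- P(exactly one) = P(SBP ≥160) + P(DBP ≥100) − 2 × P(both)
- Share of patients with any raised pressure whom the literal *and* excludes = P(both) / [P(both) + P(exactly one)]

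Middle case (SBP 130/16, DBP 78/10 as mean/SD, ρ = 0.6):

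- z for SBP = (160 − 130)/16 = 1.875, so P(SBP ≥160) = 0.0304
- z for DBP = (100 − 78)/10 = 2.2, so P(DBP ≥100) = 0.0139
- P(both) = 0.0047
- P(exactly one) = 0.0304 + 0.0139 − 2 × 0.0047 = 0.0349, made up of SBP only 0.0257 and DBP only 0.0092
- Share excluded by *and* = 0.118 from unrounded values

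Extremes over the fully crossed ranges:

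| Quantity | Extreme | SBP mean/SD | DBP mean/SD | ρ | P(both) | P(exactly one) | Share |
|---|---|---|---|---|---|---|---|
| Exactly one | minimum | 125/14 | 75/9 | 0.7 | 0.0009 | 0.0072 | 0.108 |
| Exactly one | maximum | 135/18 | 80/11 | 0.5 | 0.0129 | 0.0911 | 0.124 |
| Share | minimum | 135/18 | 75/9 | 0.5 | 0.0016 | 0.0821 | 0.019 |
| Share | maximum | 130/18 | 80/11 | 0.7 | 0.0150 | 0.0523 | 0.223 |

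So 0.7% to 9.1% of screened patients would have exactly one pressure at or above its limit. The literal *and* would exclude only 1.9% to 22.3% of those with at least one raised pressure. These figures ignore repeat measurements and any discretionary exclusion.

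**The case against.** The best reply is that the definition alone sets the exclusion. The note only permits a repeat and states no threshold of its own, so applying exclusion 5 to whichever value counts gives one answer, and 190/95 mmHg is eligible. The *and/or* might merely name the component that is out of range or remeasured: a patient at 165/105 mmHg who clears either limit on repeat is eligible under *and*. The note is also near-template wording used for other criteria, and the protocol writes *and/or* inside a criterion elsewhere, for instance in the hypertension risk factor, so *and* may be deliberate.

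Much of this is fair. The conflict is by implication, and the separate listing in Section 10.5.1 proves little alone. But the note speaks of failing criteria and lets the repeat decide eligibility, which makes little sense for a patient who was already eligible. The template comparison cuts both ways: exclusion 8 has the same kind of note for ALT and AST, and its definition does not join its limits with a bare *and*. If *and* was deliberate, the note still needs rewording.

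On safety, exclusion 20 ("A medical or situational (ie, geographical) finding that in the" investigator's opinion may compromise safety) allows such a patient to be kept out, and Section 12.1 has vital signs reviewed at every visit. These are real backstops, but they rest on judgement and set no limit. SAP 5.4.6 flags only rises of more than 15 mmHg from baseline, so a high entry pressure that stays high is not flagged, though it remains visible in the listings and summaries. That argument carries limited weight, because the flag would equally miss a stable 159/99 mmHg after the fix.

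Finally, the SAP addenda report that the planned analyses were complete, so a protocol amendment can no longer change enrolment in this trial. That limits the practical use of an amendment here; it does not make the two texts agree.

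**Conclusion.** The concern holds. Exclusion 5 and its note disagree for any patient with exactly one pressure at or above its limit, and nothing in Amendment 1 or the SAP says which governs. Taken literally, the rule leaves a clearly hypertensive patient eligible in a high-risk population.

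The mismatch is plain on the page; that *and/or* was intended is an inference, held with medium confidence. The disputed group is about 3.5% of screened patients in the middle case (0.7% to 9.1%), wholly on assumed distributions, and the importance of the point does not rest on those figures. It should be corrected, but it is minor and leaves the LDL-C comparisons, alpha and sample size untouched.

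**What to change.** In the Synopsis and in Section 7.2, redefine exclusion 5 as SBP ≥160 mmHg *and/or* DBP ≥100 mmHg, keeping the five-minute seated rest. The notes and Section 10.5.1 then need no edit.

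If the sponsor does intend both limits to be required, keep *and*, and reword the two notes and the list in Section 10.5.1 to refer to a single combined blood-pressure criterion.

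The preferred change is one connector in two places, made by formal amendment under Section 19.3. Its price is a slightly smaller eligible pool: at most the disputed group sized above, less those who pass on repeat or whom the investigator would have excluded anyway.

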7.3. Patient Lifestyle and Dietary Guidelines

Patients will fast for a minimum of 10 hours prior to collection of all laboratory samples (water and concomitant medications are permitted).

Beginning at screening, patients will be counseled to follow a heart healthy diet as per local or regional guidelines and should be encouraged (as able) to participate in a stable, regular exercise program throughout the study.

8. TREATMENT OF PATIENTS

8.1. Administration of Investigational Medicinal Product

During the Treatment Period, patients will be randomized to receive IMP of either BA 180 mg + EZE 10 mg FDC, BA 180 mg, EZE 10 mg, or placebo once daily. Each daily allotment of IMP is comprised of 2 tablets and 1 capsule provided in a blister package. Patients will be instructed to ingest IMP orally once daily with or without food at a similar time every day. On clinic visit days, patients will be instructed to delay ingestion of IMP until all study procedures have been completed.

If the patient forgets to take IMP on nonclinic visit days, it may be taken up to 12 hours later the same day. After that time, the patient should not take IMP that day and should resume ingestion of IMP the following day. Details describing the reasons for missed doses should be documented in the patient's medical records and electronic case report form (eCRF). Extra IMP is provided and can be used, if needed, prior to the next visit or to replace an allotment of IMP that cannot be used because it is lost or damaged.

Other details regarding IMP, including description, supply and control, accountability, handling, and disposal are provided in [Section 9](#).

8.2. Prior and Concomitant Medications

Patients will be questioned about their concomitant medication use at each clinic visit. All concomitant medication taken chronically or intermittently during the study must be recorded with indication, total daily dose, and start and stop dates of administration.

The Prior/Concomitant case report form (CRF) will be used to record medications, herbal remedies, vitamins, other nutritional supplements, and over-the-counter medications taken within 6 weeks prior to screening and during the study, with the exception of statins (particularly those that were not tolerated due to an adverse effect), which will be recorded if taken at any point in the past.

8.2.1. Required Medications

Patients will be required to be on maximally tolerated statin therapy with dose stable for at least 4 weeks prior to screening (Visit S1). Maximally tolerated statin includes statin regimens other than daily dosing, including no to very low doses. A patient's currently used and maximally tolerated statin therapy will be determined by the investigator based on their medical judgment and local standard of care. Available sources, including the patient's self-reported history of lipid-modifying therapy will also be considered. Statins may include:

- Atorvastatin (Lipitor[®]) (other than sponsor provided)
- Fluvastatin (Lescol[®])
- Lovastatin (Mevacor[®], AltopenTM)
- Pravastatin (Pravachol[®])

- Rosuvastatin Calcium (Crestor®)
- Simvastatin (Zocor®); please note that doses ≥ 40 mg/day are prohibited
- Pitavastatin (Livalo®)

